### 8.3.2 Calcitonin sampling (central laboratory analysis)

Blood samples for the measurement of calcitonin concentration will be drawn as per flow chart (see section  $\underline{2}$ ). Calcitonin values  $\geq 20$  ng/L will be submitted to an independent calcitonin monitoring committee of thyroid experts. The committee will provide guidance to the investigator with regards to treatment and further investigations. If a subject is screen failed for other reasons than calcitonin

Protocol		Date:	07 October 2014	Novo Nordisk
Trial ID: NN9068-4148	CONFIDENTIAL	Version:	2.0	
UTN: U1111-1154-6671		Status: Page:	Final 37 of 84	

exclusion criterion # 11 (calcitonin  $\geq$  50 ng/L), but has a value of calcitonin  $\geq$ 10 ng/L, it is recommended that they are referred to a thyroid expert for further evaluation. For details see appendix D.

### 8.3.3 Antibody sampling (special laboratory analysis)

Blood samples will be drawn as per flow chart for determination of serum antibodies to IDeg (including cross reacting antibodies to human insulin) and to liraglutide, dependent on treatment arm. Positive anti-liraglutide antibody samples will be further characterised for cross reactivity to native GLP-1.

Visit 29 samples positive for anti-liraglutide antibodies will in addition be analysed for *in vitro* neutralising effect in a cell based assay.

Blood sampling for antibody assessment should be performed prior to administering trial product.

Antibody results will not be provided to the investigator as these are not used for clinical evaluation during the trial. Instead they will be included in an analytical report after end of trial and retained at Novo Nordisk.

Please see section 24.2 for information on storage of antibody samples.

### 8.3.4 PK blood sampling (special laboratory analysis)

Blood samples for PK will be drawn as per flow chart. Blood sample(s) will be drawn once per subject per visit (no PK-profiling required). Samples will be analysed for serum concentrations of IDeg and/or plasma concentrations of liraglutide dependent of treatment arm.

The investigator must record the exact time for blood sampling in the eCRF. Blood samples for serum IDeg and plasma liraglutide levels will be collected, treated and shipped according to the description in a laboratory manual provided by the relevant laboratory.

Subjects must be instructed to write in their diary:

• Date, dose, injection site and exact clock time for injection from the previous three days of dosing and on the day of the visit, if a dose is taken *before* blood sampling

It is important to explain to the subjects the necessity of accurate diary recording as the investigator must transcribe all data into the eCRF subsequently to ensure accurate PK calculation.

The population PK analysis is outlined in section 17.5

The bio-analysis of IDeg and liraglutide will be done at a special laboratory (see attachment I), using a specific validated ELISA assay for each component developed by Novo Nordisk. Validation

Protocol Trial ID: NN9068-4148 UTN: U1111-1154-6671	CONFIDENTIAL	Date: Version: Status:	07 October 2014 2.0 Final	Novo Nordisk
		Page:	38 of 84	

documentation must be provided and a bio-analytical report must be available. PK results will not be provided to the investigator as these are not used for clinical evaluation during the trial. Instead they will be included in a bio-analytical report that will be available at data base lock and retained at Novo Nordisk.

PK samples will be destroyed no later than at the completion of the clinical trial report (CTR). Destruction of PK samples must only occur with permission from Novo Nordisk.

#### 8.4 Pancreatitis

Confirmed cases of pancreatitis should be followed up with investigations of other potential causes (tests such as gallbladder ultrasound, triglycerides, liver enzymes, detailed history of concomitant medications or alcohol).

### 8.5 Thyroid disease

Subjects scheduled for thyroidectomy (partial or total) for any reason during the trial, must be instructed to inform the investigator prior to their operation.

### 8.6 Subject diaries

At each site visit subjects will be provided with a new diary for recording of source data until next site visit. Here the diary must be collected and retained at the site as source data in accordance with section 14. From handout at a site visit a diary will hence contain source data from e.g. several telephone contacts prior to being returned at an upcoming visit.

Subjects are required to record the below source data in their diaries at the timing specified in the flow chart in section  $\underline{2}$ .

### • For all subjects:

- o Date and dose of first trial product
- o Date and dose of last trial product
- o Prior to PK sampling visits: See section 8.3.4 for source data to be recorded
- o 9-point profile SMPG values, see section 8.2.13 for source data to be recorded
- Any AEs, hypoglycaemic episodes and changes in concomitant medication since last site visit/telephone contact
- For subjects on IDeg or IDegLira:
  - o Daily pre-breakfast SMPG values
  - o Last trial product dose prior to each titration day
  - o Trial product dose to be taken after each titration day
- For subjects on liraglutide:
  - Pre-breakfast SMPG values on 3 consecutive days prior to every site visit/telephone contact

Protocol Trial ID: NN9068-4148 UTN: U1111-1154-6671	CONFIDENTIAL	Date: Version: Status:	07 October 2014 2.0 Final	Novo Nordisk
		Page:	39 of 84	i

Based on the SMPG values, the investigator/subject will assess whether the trial product dose needs adjustment according to the Titration Guideline.

The diary must be reviewed by the investigator to ensure that AEs, including any overall change in health and concomitant medication, are reported. The review of the diary must be documented either on the front page of the diary and/or in the subject's medical records.

The investigator or delegated staff must transcribe data from the diary into the eCRF after each site visit/telephone contact according to timelines in section 13.2.

If clarification of entries or discrepancies in the diaries is needed, the subject should be questioned and a conclusion made in the subject's medical record. Care must be taken not to bias the subject.

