Follow-up visit (FU)	SC	R	V	V	T	V	T	V	T	V	T	V	T	V	T	V	FU
Visit number															23		
							7		11		15		19		24 25		
							8		12		16		20		26		
	1	2	3	4	5	6	9	10	13	14	17	18	21	22	27	28	29
Time of visit (week)															21		
	-21		,	_	2		5 6		9	10	13	1.0	17	20	22	26	27
	-2	0	1	2	3	4	7	8	10 11	12	14 15	16	18 19	20	23 24	26	27
							_ ′		11		13		17		25		
Visit window (days)			±3	±3	±3	±3	±3	±3	±3	±3	±3	±3	±3	±3	±3	±3	+3
Hypoglycaemic episodes		X	X	X	X	X	X	X	X	X	X	X	X	X	X	X	X
ECG 	X															X	
Eye examination 5	X															X	
Physical examination	X															X	
Vital signs	X	X								X						X	
Antibodies		X								X						X	X
Biochemistry	X	X								X						X	
Haematology	X	X								X						X	
Hormones, calcitonin	X	X								X						X	
Lipids		X								X						X	
Urine dipstick		X								X						X	
Pregnancy test (blood sample)	X															X	
REMINDERS						•	•	•			•		•	•			
Handout ID card	X																
Handout and instruct in BG-meter use	X																
Attend visit fasting		X				X		Х		X		X		X		X	x 
IV/WRS call	X	X				X		X		X		X		X		X	Λ
Dispense trial product. Instruct																	<del>                                     </del>
and hand out Directions for Use.		X				X		X		X		X		X			
Drug accountability		X				X		X		X		X		X		X	
Handout and instruct in/collect diary	X	X	X	X		X		X		X		X		X		X	X
Collect first date and dose of trial			X														
Product  Collect last date and dose of trial		 	 	 	 				 							v	
product																X	
Confirmation of unchanged dose of metformin			X	X	X	X	X	X	X	X	X	X	X	X	X	X	
For liraglutide arm:																	
Confirmation of unchanged dose						X	X	X	X	X	X	X	X	X	X	X	
of liraglutide 																	
End of trial and sign off on case																	X
book	1	1	1	1	1	l	l	l	1	1	L		L	L			Щ

- 1. Screening must take place within 14 calendar days prior to randomisation.
- 2. For source data to be recorded in subject's diary prior to every PK sampling visit, please see section 8.3.4.
- 3. For IDeglira and IDeg arm: Daily pre-breakfast SMPG, last dose prior to titration and dose to be taken after titration must be recorded. For liraglutide arm: Pre-breakfast SMPG on 3 consecutive days prior to each visit/telephone contact must be recorded.

Protocol		Date:	07 October 2014	Novo Nordisk
Trial ID: NN9068-4148	CONFIDENTIAL	Version:	2.0	
UTN: U1111-1154-6671	CONFIDENTIAL	Status:	Final	
		Page:	14 of 84	

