### 8.2.14 Hypoglycaemic episodes

Plasma glucose should always be measured and recorded when a hypoglycaemic episode is suspected.

All plasma glucose values:

- $\leq 3.9 \text{ mmol/L or}$
- > 3.9 mmol/L when they occur in conjunction with hypoglycaemic symptoms,

should be recorded by the subject. These must be transcribed into the eCRF on the hypoglycaemic episode form throughout the trial from Visit 2 to Visit 29.

The record should include the following information:

- Date and time of hypoglycaemic episode
- The plasma glucose level before treating the episode (if available)
- Whether the episode was symptomatic
- Whether the subject was able to treat him/herself
- Date, time and dose of last trial product (OR other anti-diabetic treatment) administration prior to episode
- Type of last trial product (OR other anti-diabetic treatment) prior to episode
- Date and time of last main meal prior to episode
- Whether the episode occurred in relation to physical activity
- Any sign of fever or other disease
- Whether the subject was asleep when the episode occurred
- Whether the symptoms of the episode woke up the subject

The answer to the question: "Was subject able to treat him/herself?" must be answered "No" for an episode requiring assistance of another person to actively administer carbohydrate, glucagon, or

Protocol Trial ID: NN9068-4148 UTN: U1111-1154-6671	CONFIDENTIAL	Date: Version: Status:	07 October 2014 2.0 Final	Novo Nordisk
		Page:	35 of 84	

take other corrective actions. Plasma glucose concentrations may not be available during an event, but neurological recovery following the return of plasma glucose to normal is considered sufficient evidence that the event was induced by a low plasma glucose concentration 11.

If the question "Was subject able to treat him/herself?" is answered "No", the following information should be recorded and transcribed into the eCRF:

- Who assisted in the treatment of the hypoglycaemic episode (i.e. family/friend/co-worker or similar, paramedic, doctor or other, please specify)
- Where the treatment was administered (i.e. at home/at friends/at work or similar, in an ambulance, emergency room/hospital or other, please specify)
- Type of treatment provided by other person (i.e. oral carbohydrates, glucagon, IV glucose or other, please specify)
- Were symptoms alleviated by the administration of treatment?

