### Novo Nordisk classification of hypoglycaemia

[figure not shown]
In normal physiology, symptoms of hypoglycaemia occur below a plasma glucose level of 3.1 mmol/ $L^{16}$ . Therefore, Novo Nordisk has included hypoglycaemia with plasma glucose levels below this cut-off point in the definition of BG confirmed hypoglycaemia.

Novo Nordisk uses the following classification (in addition to the ADA classification):

• Severe or BG confirmed symptomatic hypoglycaemia: An episode that is severe according to the ADA classification or BG confirmed by a plasma glucose value <3.1 mmol/L with symptoms consistent with hypoglycaemia

Protocol Trial ID: NN9068-4148 UTN: U1111-1154-6671	CONFIDENTIAL	Date: Version: Status: Page:	07 October 2014 2.0 Final 68 of 84	Novo Nordisk
---	--------------	---------------------------------------	---	--------------

• Severe or BG confirmed hypoglycaemia: An episode that is severe according to the ADA classification or BG confirmed by a plasma glucose value <3.1 mmol/L with or without symptoms consistent with hypoglycaemia

[figure not shown]

Note: Glucose measurements are performed with capillary blood calibrated to plasma equivalent glucose values

Figure 17-1 Novo Nordisk classification of hypoglycaemia

# ADA classification of hypoglycaemia 11

- Severe hypoglycaemia: An episode requiring assistance of another person to actively administer carbohydrate, glucagon, or take other corrective actions. Plasma glucose concentrations may not be available during an event, but neurological recovery following the return of plasma glucose to normal is considered sufficient evidence that the event was induced by a low plasma glucose concentration
- Asymptomatic hypoglycaemia: An episode not accompanied by typical symptoms of hypoglycaemia, but with a measured plasma glucose concentration ≤ 3.9 mmol/L
- Documented symptomatic hypoglycaemia: An episode during which typical symptoms of hypoglycaemia are accompanied by a measured plasma glucose concentration ≤ 3.9 mmol/L
- Pseudo-hypoglycaemia: An episode during which the person with diabetes reports any of the typical symptoms of hypoglycaemia with a measured plasma glucose concentration > 3.9 mmol/L but approaching that level
- Probable symptomatic hypoglycaemia: An episode during which symptoms of hypoglycaemia are not accompanied by a plasma glucose determination but that was presumably caused by a plasma glucose concentration ≤ 3.9 mmol/L

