# Figure 17–2 ADA classification of hypoglycaemia

Data on treatment emergent hypoglycaemic episodes are presented in terms of the number of subjects with at least one event (N), the percentage of subjects with at least one event (%), the number of events (E) and the event rate per 100 years (R).

Separate summaries are made for severe or BG confirmed hypoglycaemic episodes, severe or BG confirmed symptomatic hypoglycaemic episodes, nocturnal severe or BG confirmed hypoglycaemic episodes, nocturnal severe or BG confirmed symptomatic hypoglycaemic episodes and the ADA classification of hypoglycaemia.

All endpoints based on hypoglycaemic episodes will be analysed using the same model as used for the treatment emergent severe or BG confirmed hypoglycaemic episodes.

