# 1 Introduction

The goal of insulin therapy is to achieve near normoglycaemia, i.e. to reach a pre-defined HbA1c level with a low rate of hypoglycaemic episodes and as little weight gain as possible. Several trials have shown that this is difficult to achieve, unless plasma glucose (PG) values are intensively monitored and the insulin dose(s) frequently adjusted 1-7.

To ensure treatment uniformity between the sites, as well as to ensure that subjects receive an optimal treatment, titration algorithms have been developed specifying recommended dose adjustments at different PG levels.

It is recognised that treatments differ between different regions and countries. Likewise, specific titration guidelines may not be applicable in certain clinical situations. It is important that other information, such as symptoms of hypo/hyperglycaemia, previous response to dose adjustments, other glucose measurements and other indicators of the subject's level of glycaemic control, is taken into consideration when decisions on dosing are made. The investigator should always use his clinical judgement to avoid safety hazards. The investigator is responsible for the treatment of the subjects and can therefore overrule the guideline.

To optimise and maintain glycaemic control, the investigator should, throughout the trial be at least in weekly contact with the subjects to assist the subjects in adjusting insulin doses and to ensure the subjects' welfare.

Protocol - Appendix A		Date:	07 October 2014	Novo Nordisk
Trial ID: NN9068-4148	CONFIDENTIAL	Version:	2.0	
UTN: U1111-1154-6671	CONFIDENTIAL	Status:	Final	
		Page:	4 of 8	

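### Supportive hypoglycaemia contrasts of IDegLira with liraglutide that count asymptomatic readings are open to unequal detection: 182 versus 78 scheduled fasting tests, with an offset that adjusts for time only

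*Protocol*

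**What the plan says.** **Testing schedule.** Section 8.6 (Subject diaries) requires "Daily pre-breakfast SMPG values" from subjects on IDeg or IDegLira, and "Pre-breakfast SMPG values on 3 consecutive days prior to every site visit/telephone contact" from subjects on liraglutide. A flow chart footnote repeats the difference: "For liraglutide arm: Pre-breakfast SMPG on 3 consecutive days prior to each visit/telephone contact must be recorded". The flow chart places Visits 3 to 28 at weeks 1 to 26. Appendix A, section 1, asks the investigator to "throughout the trial be at least in weekly contact with the subjects".

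**From reading to episode.** Section 8.2.14 has subjects in every arm record any value at or below 3.9 mmol/L: "These must be transcribed into the eCRF on the hypoglycaemic episode form throughout the trial from Visit 2 to Visit 29". In section 17.4.2.2 the sponsor's own class includes an episode that is "BG confirmed by a plasma glucose value <3.1 mmol/L with or without symptoms consistent with hypoglycaemia". The ADA asymptomatic class is "An episode not accompanied by typical symptoms of hypoglycaemia, but with a measured plasma glucose concentration ≤ 3.9 mmol/L".

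**Model.** Section 17.4.1 specifies a negative binomial model whose offset is the log of the treatment-emergent time. Section 17.4.2.2 extends it: "All endpoints based on hypoglycaemic episodes will be analysed using the same model".

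**Contrasts.** Section 4.1.2 includes a safety comparison of IDegLira with both IDeg and liraglutide. Section 17.4.2.1 says both treatment contrasts will be estimated for the supportive efficacy endpoints. Four of these are HbA1c responder endpoints that require no severe or BG confirmed episode in the last 12 weeks. The confirmatory hypoglycaemia test in section 17.4.1 is against IDeg only.

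**The concern.** An asymptomatic low value enters the data only if the subject happens to test. An arm that tests every morning has more chances to find one than an arm scheduled to test on three mornings a week. The offset corrects for how long a subject was observed, not for how often the subject looked.

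Three groups of endpoints are exposed in the comparison with liraglutide: the severe or BG confirmed rate, the ADA asymptomatic rate, and the four composite responders. For the rates, the ratio is pushed up for IDegLira. For the responders, a subject who tests more often is more likely to lose responder status. The trial is meant for registration of a combination product and includes liraglutide so that benefit and risk can be judged against each component (sections 3.2 and 5.6). A shift of known direction and unknown size in that comparison should be dealt with in advance.

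**Working it through.** The protocol gives no figure for hypoglycaemia rates or test frequency, so there is no stated value to reproduce on this point. Its only computed design figure, the power for HbA1c, does reproduce but has no bearing here.

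**1. Scheduled fasting tests over 26 weeks** (section 8.6 and flow chart)
- IDegLira and IDeg: 26 × 7 = 182
- Liraglutide: 26 contacts × 3 = 78
- Ratio: 182/78 = 2.33; the liraglutide arm has 78/182 = 43% of the tests

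**2. Adding the 9-point profiles.** All arms perform two after baseline (Visits 14 and 28). Each has seven points that are not pre-breakfast readings, so 14 are added per arm: 196 against 92, ratio 2.13.

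**3. Last 12 weeks** (window for the composite responders): 12 × 7 = 84 against 12 × 3 = 36 scheduled fasting tests.

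**4. Expected rate ratio when the true rates are equal.** Let s be the share of episodes, as counted under daily testing, that are asymptomatic and found only by the scheduled fasting test. Assume that no such episode is found on liraglutide outside its scheduled days. Then

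RR = 1 / [(1 − s) + s × 78/182]

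| s (assumed) | Denominator | Expected RR, IDegLira/liraglutide |
|---|---|---|
| 0% | 1.000 | 1.00 |
| 10% | 0.943 | 1.06 |
| 25% | 0.857 | 1.17 |
| 50% | 0.714 | 1.40 |
| 100% | 0.429 | 2.33 (upper limit) |

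**5. Effect on a nominal two-sided 5% test.** Illustration with 360 against 180 subjects, 0.5 year, and assumed values of 0.5 episodes per year and dispersion 3. A true null would be rejected 5.7% of the time at s=10%, 9.5% at 25% and 25% at 50%.

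**6. Composite responders.** The formula in step 4 is for rates and cannot be applied to proportions. A rough Poisson illustration at the same assumed 0.5 episodes per year gives an expected 0.5 × 12/52 = 0.115 episodes in 12 weeks under daily testing.
- IDegLira episode-free share: exp(−0.115) = 89.1%
- Liraglutide at s=25%: exp(−0.115 × 0.857) = 90.6%
- Liraglutide at s=50%: exp(−0.115 × 0.714) = 92.1%

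The gap is 1.5 to 3 percentage points before the HbA1c and weight conditions are applied.

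**7. Contrast with IDeg.** Both arms have 182 scheduled fasting tests, so the schedule-driven factor is 1.00.

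**The case against.** **What stands.**
- The affected contrasts are supportive, and the shift works against IDegLira, so it cannot create a false advantage for it. Section 5.6 does not list hypoglycaemia among the expected benefits over liraglutide.
- The rate contrast with liraglutide is inferred. The sentence promising both contrasts opens the efficacy subsection (17.4.2.1), so it covers the composite responders directly. For the rates, it must be read together with section 4.1.2 and the same-model statement in 17.4.2.2.
- The value of s appears nowhere and may be near zero. The liraglutide schedule is a minimum for recording, not a ban on testing. Every subject has a meter and must record any low value, so off-schedule tests dilute the effect, as do the profiles.
- The symptomatic endpoint is already planned and will be reported beside the others.
- The amendment dated 31 August 2016 (section 2.1.15) revised the hypoglycaemia definitions in text that is not shown. The amendment dated 28 September 2016 keeps the severe or BG confirmed endpoint and the time offset. No amendment text that is shown alters the testing schedule.

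**What does not stand** is the argument that this is only detail for the analysis plan. The protocol itself fixes the schedule, the definitions, the model and the offset, and following them as written produces the tilt.

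**Stronger readings a reader might infer.** One is that IDegLira will necessarily show an excess over liraglutide, or one as large as 2.33-fold. The documents do not support this: 2.33 would require every episode to be found only by a scheduled fasting test, with no off-schedule detection on liraglutide. Another is that the confirmatory hypoglycaemia result or its type I error is compromised. It is not, because that test compares two arms with the same daily schedule.

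**Conclusion.** The point holds as a risk of differential ascertainment in the supportive contrasts of IDegLira with liraglutide, limited to definitions that count asymptomatic readings. The direction is fixed by the protocol and is against IDegLira. The size cannot be computed from the protocol. Under the step 4 assumptions it is an expected rate ratio of 1.00 to 1.40 for s from 0% to 50%. For the composite responders it is probably a few percentage points at most at the assumed episode rate.

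Severe or BG confirmed symptomatic endpoints do not count asymptomatic readings. Nocturnal endpoints (00:01 to 05:59) are less exposed, because a pre-breakfast test usually falls later. The confirmatory contrast with IDeg and the testing hierarchy are untouched. The point merits correction because the remedy is cheap, not because a primary conclusion is at risk.

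**What to change.** In section 17.4.2, for contrasts with liraglutide:
1. Name the existing severe or BG confirmed symptomatic endpoint as the leading hypoglycaemia comparison.
2. For definitions that include asymptomatic episodes, both rates and the four composite responders, add an analysis that counts asymptomatic pre-breakfast episodes only if they fall on the three days before a contact, in all arms.
3. State the unequal testing schedule as a limitation of the unrestricted results.

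Leave the definition and model for the contrast with IDeg as they are. Testing and treatment of subjects do not change.

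The data are already collected: section 8.2.14 records the date and time of each episode, and section 14.1 makes the diary the source for the dates and values of fasting readings. The episode form has no field saying whether a reading was a scheduled test, so episodes must be matched to diary readings and contact dates by date and time.

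The cost is one extra derivation, a separate model run per affected endpoint, and fewer counted episodes, hence less precision, in the liraglutide contrast. The restriction removes most of the bias but not all of it, because off-schedule testing at other times of day may still differ between arms.
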